5.10.4 Other sensitivity analyses

The COVID-19 pandemic has impacted clinical development and ongoing clinical trials. Public Health measures to control the virus may impact the ability to collect data. Additionally, the number of HF admissions were reduced by 40% in Europe between March and June 2020. The change in patient behaviours and characteristics might lead to for example less hospitalizations, more advanced HF presentations, less hospital admission duration, and less protocol adherence which all might impact study results.

Several mitigation strategies were discussed in the steering committee meeting. (a) Extra efforts to capture potential reasons for missing data will be employed. (b) Due to slower enrolment extension of the trial was considered until complete enrolment of the predefined sample size. The trial completion was achieved before the expiration date of the Investigational Medicinal Product (IMP).

Because of the aforementioned potential differences in patient characteristics, a sensitivity analysis for the primary endpoint will be performed.

The treatment effect for the primary endpoint is evaluated by means of a generalized linear mixed model, including a fixed treatment effect and random centre effect. As a sensitivity analysis, the model will be extended by including a fixed effect (binary) indicating if the endpoint was assessed before or after the first identified COVID-19 case in Belgium dated 03 February 2020 and the interaction term between this variable and treatment.

5.11 Analysis of secondary outcomes

All statistical models implemented for the analysis of the secondary outcomes are mixed-effects models, including a fixed treatment effect and random centre effect. For the outcomes measured at multiple time points also random patient effects (intercept, slope) are included.

5.11.1 Secondary outcome 1

The combined endpoint of all-cause mortality and HF readmission during 3 months of follow-up, will be analysed as a binary and as a time-to-event endpoint.

- For descriptive purposes, the number (%) of failure and success for the combined outcome of all-cause mortality and HF readmission during 3 months of follow-up will be given per treatment arm. To investigate the treatment effect on the occurrence of the combined endpoint, a generalized linear mixed model for a binary outcome will be employed. The model will incorporate a fixed treatment effect and random centre effect. The results of this model will be presented as odds-ratio, 95% confidence interval and the associated p value.

If the treatment effect on the composite endpoint of 'all-cause mortality and HF readmission' turns out to be statistically significant, both components will be evaluated separately in a hierarchical fashion with HF readmissions first and all-cause mortality second. For this analysis, HF readmission will include patients dying from any cause during the 3 months of FU. The treatment effect, on the components, will be investigated by the same statistical model as used for the combined endpoint.

- To investigate the treatment effect on the time until combined endpoint of all-cause mortality and HF readmission during 3 months of follow-up a survival analysis will be performed. Time to event is defined as the time between day 1 and the date of (first) HF readmission or death if there was no HF readmission. The analysis will be censored at 3 months of follow-up or at the time when the patient was last known to be alive (for patients that withdraw or are lost to follow up), whichever occurs earlier. Survival times will be summarised descriptively using Kaplan-Meier survival curves. Formal testing for a difference in time to event will be done using a mixed-effect Cox proportional hazard model including the treatment arm and a random centre effect (ie, using a shared frailty model). The proportional hazards assumption will be verified by plotting log cumulative hazard versus log-time for the intervention and SOC group. Model validity will be further explored using plots of Cox-Snell and Martingale residuals. The treatment effect will be summarised as the hazard ratio (HR), 95% CI and associated p value.

To assess whether the treatment effect differs according subgroups defined on the basis of LVEF (see table in section 5.10.2) a subgroup analysis will be performed. The statistical model formulated for the analysis of this endpoints (binary and time to event version) will be extended to include a fixed effect for the subgroup and an interaction term between the study arm and the subgroup. The interaction term will be considered significant at the 5% level. Within each subgroup, summary statistics of the outcome by treatment arm will be presented; the OR/HR for the treatment effect and 95% confidence interval. A p-value for the interaction test will also be reported.

5.11.2 Secondary outcome 2

For each treatment arm mean, median and interquartile range for length of index hospitalization will be presented for patients who survived to hospital discharge. The effect of treatment on length of index hospitalization, for patients who survived to hospital discharge, is compared among treatment arms with a linear mixed model⁸ (fixed treatment effect and random centre effect). A log transformation will be employed as the model assumptions (such normality) will likely be violated. Model assumptions will be investigated by means of diagnostic plots. The results of this model will be presented as (geometric) mean length of index hospitalization (and 95% CI) per treatment group, the geometric mean ratio (GMR), 95% CI and associated p value.

To assess whether the treatment effect differs according subgroups defined on the basis of LVEF (see table in section 5.10.2) a subgroup analysis will be performed. The statistical model formulated for the analysis of this endpoint will be extended to include a fixed effect for the subgroup and an interaction term between the study arm and the subgroup. The interaction term will be considered significant at the 5% level. Within each subgroup, summary statistics of the outcome by treatment arm will be presented; the GMR for the treatment effect and 95% confidence interval. A p-value for the interaction test will also be reported.

5.11.3 Secondary outcome 3

The QoL scores (EQ-5D total score and EQ-VAS) will be presented using line plots for each study arm to illustrate trends over time. Depending on the distribution of the data, the means and 95% CI of means or medians and inter-quartile ranges at baseline, the morning of day 4 or discharge (whatever comes first), and at 3 months of follow up will be reported. Evolution in the QoL will be investigated via a linear mixed model, with the QoL score of morning of day 4 or discharge (whatever comes first), and 3 months follow up as the longitudinal dependent variable, with a fixed treatment effect, day, the interaction of treatment by day, and baseline QoL, random centre effect and random patient effect (intercept, slope) will be used. Model assumptions will be investigated by means of diagnostic plots. Transformation will be employed when the model assumptions (such normality) are violated.

The analysis will be performed following the recommendations of the Belgian guidelines for health economic evaluation to value health care resource use will be used:

<https://kce.fgov.be/nl/een-belgische-waardenset-voor-de-eq-5d-5l-%E2%80%93-hoe-gezondheidsgerelateerde-levenskwaliteit-waarderen>

A subgroup analysis with subgroups defined on the basis of LVEF, will also be performed.

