3.6 Exploratory tertiary endpoints

1. Body weight change after day 1, 2, 3, 4 and discharge compared to screening
2. All-cause mortality during first 3 months after study start dose
3. Heart failure readmissions during first 3 months after study start dose
4. All cause rehospitalisation during first 3 months after study start dose
5. Total urinary volume and natriuresis starting from first intravenous (IV) diuretic administration at randomization until the morning of day 3
6. Relative plasma BNP or NT-proBNP change from screening until day 4 or at discharge (whatever comes first) and at 3 months follow up visit
7. Total dose of IV loop diuretics used during first 4 days
8. Changes in doses of neurohumoral blockers from baseline to discharge and after 3 months.
9. Need for renal replacement therapy or ultrafiltration during first 3 months after study start dose
10. Hyponatremia during treatment phase
11. Hypokalaemia during treatment phase
12. Incidence of metabolic acidosis requiring NaHCO₃ supplements during first 4 days
13. WRF defined as a >0.3 mg/dL increase in serum Cr, or a >20% decrease in eGFR by the CKD-EPI formula during treatment phase
14. Liver dysfunction at screening
15. plasma volume changes during treatment phase (assessed by albumin and hematocrit)
16. Occurrence of iron deficiency at screening
17. Optional laboratory sub-study in participating centers: Change from screening in selected biomarkers from baseline through 3 months after study start dose in a subset of randomized patients

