10.3 Statistical analysis plan

- The treatment effect for the primary end-point [Treatment success (decongestion achieved) on the morning of day 4 without escalating diuretic strategy (doubling loop diuretic dose, addition of chlorthalidone, or ultrafiltration) during IV diuretic therapy on morning of day 3 is evaluated by means

of a generalized linear mixed model. The statistical model will include a fixed treatment effect and random center effect.

- For the first secondary end-point [occurrence of the combined endpoint of all-cause mortality and heart failure readmission during 3 months of follow-up], a generalized linear mixed model for a binary outcome will be used. The model will incorporate a fixed treatment effect and random center effect. If the treatment effect on the composite endpoint of 'all-cause mortality and HF readmission' turns out to be statistically significant, both components will be evaluated separately in a hierarchical fashion with HF readmissions first and all-cause mortality second. For this analysis, HF readmission will include patient dying from HF during the 3 months of FU. As a sensitivity analysis the worst case scenario, assuming a HF readmission for all patients dying to non HF related causes during the 3 month follow-up will be executed.
- Length of index hospitalization and change in quality of life scores are compared among treatment arms with a linear mixed model (fixed treatment effect and random center effect). Transformation will be employed when the model assumptions (such normality) are violated.
- All hypothesis are 2-sided and tested with a significance level of $\alpha=0.05$.

The proposed statistical models all assume the missing data mechanism to be missing at random. To investigate the sensitivity of the conclusions with respect to this assumption, a sensitivity analysis by means of multiple imputation technique will be performed.

Secondary Analysis:

- All statistical models discussed in the secondary analysis include a fixed treatment effect and random effect for the center, and in case of longitudinal outcome random patient effects (intercept, slope).
- The mixed models for the primary and secondary end-point analyses will be extended with explanatory variables (such as gender, age, race, ethnicity, kidney function, neurohumoral blockers, diuretics and blood pressure)
- For the end-points collected repeatedly over time, the rate of change will be investigated using longitudinal data models.

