4.1.4 Safety objectives and endpoints

Safety Objective	Safety Endpoints
To evaluate the safety of the combination therapy with acetazolamide in this patient population.	
 - Severe metabolic acidosis at any time during study treatment - Doubling or more ($\geq 2x$) of baseline serum Creatinine, or $\geq 50\%$ decrease in baseline eGFR at any time during study treatment - Hypokalaemia at any time during study treatment - Hypotension at any time during study treatment

Definition of Safety endpoints

- Severe metabolic acidosis: a value of bicarbonate < 12 mmol/L at any time during study treatment (day 1- day 4)
- Worsening of eGFR or the need for renal replacement therapy during the index hospitalization. eGFR is obtained via the CKD-EPI formula. The eGFR values will be calculated (in mL/min/1.73 m²) from the local laboratory creatinine measurements using the CKD-EPI formula (Levey et al 2009)².
- Hypokalaemia: a value of potassium $\leq 3,0$ mmol/L at any time during study treatment (day 1- day 4)
- Hypotension: a value of systolic blood pressure < 85 mmHg at any time during study treatment (day 1- day 4)

Baseline laboratory value

For all laboratory variables, the baseline value is defined as the last value prior to the first dose of study drug.

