4.1.5 Exploratory objectives and endpoints

Exploratory Objectives	Exploratory endpoints
To determine whether acetazolamide compared with placebo in combination with loop diuretics will have an effect on body weight.	Change in body weight.
To determine whether acetazolamide compared with placebo in combination with loop diuretics will reduce the incidence of all cause rehospitalisation's.	All cause rehospitalisation during first 3 months after study start dose.
To determine whether acetazolamide compared with placebo in combination with loop diuretics will have an effect on total urinary volume and natriuresis.	Total urinary volume and natriuresis starting from first intravenous (IV) diuretic administration at randomization until the morning of day 3.
To determine whether acetazolamide compared with placebo in combination with loop diuretics will have an effect on plasma natriuretic peptides.	Change in plasma natriuretic peptides change from screening until day 4 or at discharge (whatever comes first) and at 3 months follow up visit.
To determine whether acetazolamide compared with placebo in combination with loop diuretics will have an effect on the total dose of IV loop diuretics used during first 4 days.	Total dose of IV loop diuretics used during first 4 days.
Effect of decongestion on uptitration of neurohormonal blockers	Changes in doses of neurohumoral blockers.
To determine whether acetazolamide compared with placebo in combination with loop diuretics will reduce the need for renal replacement therapy.	Need for renal replacement therapy or ultrafiltration during first 3 months after study start dose.
To determine whether acetazolamide compared with placebo in combination with loop diuretics will reduce the incidence of hyponatremia during treatment phase.	Hyponatremia during treatment phase.
To evaluate if liver dysfunction at screening has an effect on the treatment effect on the primary endpoint.	Liver dysfunction at screening and primary endpoint.
To determine whether acetazolamide compared with placebo in combination with loop diuretics will have an effect on plasma volume changes during treatment phase.	Change in plasma volume during treatment phase (assessed by albumin and hematocrit)

Exploratory Objectives	Exploratory endpoints
To evaluate if iron deficiency at screening has an effect on the treatment effect on the primary endpoint	Iron deficiency at screening and primary endpoint

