5.3 Multiplicity adjustment

There will be no correction for multiplicity of testing as there is only one primary endpoint. All other endpoints and subgroup analyses will be considered as exploratory.

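### SAP v2.0 names a separate comparison of deaths only after a significant composite, drops two unconditional protocol endpoints, and defines HF readmission so that it equals the composite

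*Combined protocol and SAP*

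**What the plan says.** **The condition.** SAP v2.0 section 5.11.1 always gives counts by arm and an odds ratio for the composite, and a hazard ratio from a Cox model. The components follow only if the composite effect "turns out to be statistically significant, both components will be evaluated separately in a hierarchical fashion with HF readmissions first and all-cause mortality second". Protocol v2.0 section 10.3 contains the same condition.

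**The protocol endpoints.** Protocol 3.6 lists "All-cause mortality during first 3 months after study start dose" (no. 2) and "Heart failure readmissions during first 3 months after study start dose" (no. 3), neither of them conditional on anything.

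**The SAP list.** SAP 4.1.5 restates the exploratory endpoints. It keeps the neighbouring item, "All cause rehospitalisation during first 3 months after study start dose", and contains neither no. 2 nor no. 3. The SAP document history records no withdrawal.

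**Safety.** SAP 4.1.4 opens with "Severe metabolic acidosis at any time during study treatment" and goes on to renal function, hypokalaemia and hypotension. Death is not among the outcomes, and section 5.12 analyses only those listed.

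**Multiplicity.** SAP 5.1 rules out any correction for multiple testing. SAP 5.3 adds: "All other endpoints and subgroup analyses will be considered as exploratory".

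**The component definition.** SAP 5.11.1: "For this analysis, HF readmission will include patients dying from any cause during the 3 months of FU". Protocol 10.3: "For this analysis, HF readmission will include patient dying from HF during the 3 months of FU". The protocol keeps the version that also counts non-HF deaths for a worst-case sensitivity analysis.

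**The concern.** A composite of death and readmission can be null because nothing happened, because the trial was too small, or because its parts moved in opposite directions. Only separate figures for the parts can tell these apart. The SAP withholds them in exactly the case where they are needed. Mortality is also not a side issue in this plan: the first secondary objective in SAP 4.1.3 names lower all-cause mortality and fewer HF readmissions.

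An ordered, conditional test of components normally serves to control type I error. Here nothing outside the primary endpoint is controlled, so the condition buys no such protection. Followed to the letter, it decides whether an estimate is produced at all.

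**Working it through.** **1. Where deaths appear by arm in SAP v2.0**

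- Composite odds ratio and Cox hazard ratio (5.11.1): unconditional, deaths pooled with readmissions.
- Mortality component (5.11.1): only after a significant composite.
- Exploratory list (4.1.5) and safety outcomes (4.1.4, 5.12): absent.
- Length of stay (5.11.2): restricted to patients who survived to discharge.

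So there is no unconditional, separate mortality estimate.

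**2. What the HF-readmission component is**

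Let D be death from any cause and R be HF readmission, both within 3 months.

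- Composite: D or R.
- SAP component: R, with every D added, which is again D or R.
- Protocol component: R, with HF deaths added.

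The SAP component is the same patient-level event as the composite and uses the same model, so it returns the same odds ratio, interval and p value. The first step of the hierarchy therefore always passes once the composite is significant. R on its own is analysed nowhere in the SAP.

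**3. How often the condition would fail**

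*Sample size.* The plan's figure reproduces. With 15% against 25%, two-sided 5% and 80% power, the unpooled formula gives (1.96 + 0.84)² × (0.15 × 0.85 + 0.25 × 0.75) / 0.10² = 247.2 per arm with unrounded quantiles; 2 × 247 = 494, and 494 × 1.05 = 518.7, or 519. At 1:1 this is n = 259.5 per arm.

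*Assumed.* A control composite rate of 20 to 40%, since the documents give none. The 25% relative reduction is the one protocol 10.4 hopes for in HF rehospitalisation, here applied to the whole composite.

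*Formula* (two proportions, centre effect ignored): power = Φ[(|p₁ − p₂| − 1.96·s₀) / s₁], with s₀ = √(2p̄(1 − p̄)/n) and s₁ = √((p₁(1 − p₁) + p₂(1 − p₂))/n).

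*Example at 30% against 22.5%.* p̄ = 0.2625, s₀ = 0.0386, s₁ = 0.0385. Power = Φ[(0.075 − 0.0757)/0.0385] = Φ(−0.02) = 0.49.

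| Control | Acetazolamide | Composite significant | Not significant |
|---|---|---|---|
| 20% | 15% | 32% | 68% |
| 25% | 18.75% | 41% | 59% |
| 30% | 22.5% | 49% | 51% |
| 35% | 26.25% | 58% | 42% |
| 40% | 30% | 67% | 33% |

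With the 11.7% reduction that protocol 10.4 also mentions, the composite is significant in only 10 to 20% of trials over the same range. If only readmission without death falls by 25% (20% to 15%, deaths 10% in both arms, so composite 30% against 25%), simulation of 20,000 trials with 260 per arm gives 25%.

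**4. What an unconditional mortality row would show**

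With equal death rates d in the two arms, the 95% CI for the odds ratio is about exp(±1.96·√(2[1/(nd) + 1/(n(1 − d))])):

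- d = 5%: 0.45 to 2.20
- d = 10%: 0.56 to 1.77
- d = 15%: 0.62 to 1.62

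An offsetting case, chosen only as an illustration: deaths 8% control against 15% acetazolamide, readmission without death 22% against 15%, composite 30% in both arms. In the same kind of simulation the composite is significant in 5% of trials and a direct comparison of deaths in 72%. In 69% of trials deaths differ significantly while the composite does not.

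**The case against.** **The protocol still stands.** Protocol 3.6 was not withdrawn, and the SAP says that it follows protocol v2.0. SAP 5.1 asks for numbers, a summary by arm, an effect estimate and a 95% CI for each exploratory outcome. Read together, these could support a mortality table whatever the composite shows. This is enough to defeat the reading that deaths would never be compared. It does not close the gap: SAP 4.1.5 is the SAP's own list of exploratory outcomes and leaves mortality out, while 5.11.1 makes it conditional.

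**Scope.** The SAP limits itself to the primary and secondary objectives. That explains little, since it lists the other tertiary endpoints and its own first secondary objective names both components.

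**The condition was prespecified.** It is in the protocol too, and it can reasonably restrain formal claims. That stands, but restraining a claim does not require withholding an estimate.

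**HF readmission elsewhere.** Protocol 10.3 plans recurrent-event models for repeated HF readmissions without this condition. That is correct, so the documents as a whole do not make every analysis of readmission conditional. The SAP, however, does not carry those models over.

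**Oversight.** The trial has no DSMC and no interim analysis, from which a reader might infer that nobody watches deaths. The protocol has deaths reported within 5 working days, adjudicated, and safety data reviewed periodically by the Trial Steering Committee. The point concerns the final analysis.

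**Precision.** A mortality comparison in 519 patients would be imprecise, as the intervals above show. That is a reason to give the interval.

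**Conclusion.** The point holds in this form: after a non-significant composite, SAP v2.0 names no separate by-arm mortality estimate, contrary to protocol 3.6, and it analyses HF readmission proper in no case. Both statements follow from the text alone and need no assumed rates.

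The size rests on assumptions. Under control rates of 20 to 40% and a 25% reduction in the whole composite, the condition fails in about 33 to 68% of trials, and more often with smaller effects.

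Two stronger readings are not supported. One is that a null composite leaves deaths out of every comparison: they remain in the composite odds ratio and hazard ratio, and the protocol endpoint still exists. The other is that a null composite would point to opposing effects. Protocol 13.3 itself says that hard endpoints would need thousands of patients, so low power is the ordinary explanation. The offsetting example shows what could be missed, not what is expected.

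The primary analysis, its alpha and the sample size are unaffected. This is a free improvement.

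**What to change.** 1. In SAP 4.1.5, restore all-cause mortality and HF readmission at 3 months as protocol endpoints 2 and 3.
2. In SAP 5.11.1, state that each is reported by arm with count, effect estimate and 95% CI whatever the composite shows.
3. For this report, define HF readmission without adding deaths from any cause, and reconcile the component definition in SAP 5.11.1 with protocol 10.3. Deleting the significance condition while leaving the present definition would only print the composite twice.
4. If the hierarchical order is kept, let it govern formal significance claims only.

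The cost is SAP wording and two table rows. The protocol already has these events collected and adjudicated.

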4.1.3 Secondary objectives and endpoints

Secondary Objectives	Secondary Endpoints

To investigate if combination therapy with acetazolamide:
 
 - leads to improved clinical outcome in decompensated HF (less HF readmissions, lower all-cause mortality) - shortens the length of stay in patients with decompensated HF, which is expected to reduce health care expenditure - leads to improved quality of life 	
 - Combined endpoint of all-cause mortality and HF readmission during 3 months of follow-up - Length of index hospital admission - Change in EuroQoL

Definition of secondary endpoints

- The combined endpoint of all-cause mortality and HF readmission during 3 months of follow-up is a binary endpoint. The time to the combined endpoint will be calculated as the time between start of study medication (day 1) and the date of (first) HF readmission or mortality (whichever comes first). *HF readmission* is defined as either a hospital admission or an unscheduled contact at the emergency department and when

treatment with intravenous loop diuretics is initiated because of worsening HF.

- Length of index hospital admission (calculated in days) is obtained as the date of discharge from the hospital minus the date of screening +1.
- EuroQol is a five dimension patient-reported QoL questionnaire (EQ-5D-5L). The EQ-5D-5L health states, defined by the EQ-5D-5L descriptive system, are converted into a single index value (<https://kce.fgov.be/nl/een-belgische-waardenset-voor-de-eq-5d-5l-%E2%80%93-hoe-gezondheidsgerelateerde-levenskwaliteit-waarderen>). The VAS assessment of the EQ-5D will also be used. The EQ VAS records the patient's self-rated health on a vertical visual analogue scale.

The index values and EQ-VAS at baseline, the morning of day 4 or discharge (whatever comes first), and at 3 months of follow-up will be used for the secondary objective.

During the study the baseline EQ-5D-5L questionnaire has been completed as soon as possible after screening up to day 1.

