5 STATISTICAL ANALYSIS

5.1 General principles

This statistical analysis plan dated 17 January 2022 is based on the statistical information documented in the study protocol version 2.0 dated 03 January 2019 (see section 10), the methods paper published in the European Journal of Heart Failure (2018)³ and guidance by the European Medicines Agency (EMA)⁴ and the Food and Drug Administration⁵ regarding the management of clinical trials during COVID-19 pandemic (2021).

The scope of this statistical analysis plan is to outline the statistical tools used for the primary and secondary objectives of the ADVOR study following the procedures documented in the study protocol version 2.0 dated 03 January 2019 in all participating centres.

Prior to the statistical analysis the collected study data will be cleaned by the data management team of the Clinical Trial Unit at the Ziekenhuis Oost-Limburg (ZOL-CTU). The cleaning will be performed according to the Data Management Plan agreed for the ADVOR trial.

All statistical hypothesis are 2-sided and a 5% significance level will be used. A correction for multiple testing will not be implemented.

Trial results will be reported according to the CONSORT statement on reporting randomized controlled trials.

For the analysis of the primary outcome, each secondary and exploratory outcome the following information will be presented:

- the number of patients included in each analysis, by treatment arm
- a summary statistic of the outcome (e.g. number (%), mean (SD)), by treatment arm

- the estimated treatment effect
- a 95% confidence interval for the estimated treatment effect
- A two-sided p-value for all analyses, a significance level of 5% will be used.

All statistical analysis will be done with Statistical Analysis System (SAS) for Windows, SAS 9.4.

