5.5 Data sets to be analysed

For the *primary endpoint* the statistical analysis will be based on an intention-to-treat analysis set (ITTAS) including all randomized patients. Patients will be analysed according to the treatment group they were allocated to according to the electronic randomization system (irrespective of the actual treatment received).

For the *secondary endpoints* the statistical analyses will be based on the same data set as will be used for the primary endpoint analysis.

For the *safety endpoints*, all patients that were randomized and received at least 1 dose of the investigated drug or placebo will be included (safety population). For the safety analysis, patients will be grouped based on the actual study treatment received.

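### The SAP counts every death as an HF readmission, so the first component test repeats the composite and departs from protocol 10.3 with no reason given

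*Combined protocol and SAP*

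**What the plan says.** SAP v2.0 section 4.1.3 defines the first secondary endpoint as a binary composite of death from any cause or HF readmission within 3 months. It defines an HF readmission as an admission or unscheduled emergency visit at which intravenous loop diuretics are started for worsening HF. Death is not part of that definition. The objective behind the endpoint is that treatment "leads to improved clinical outcome in decompensated HF (less HF readmissions, lower all-cause mortality".

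Section 5.11.1 tests the components only if the composite is significant, HF readmission first and all-cause mortality second. It then adds: "For this analysis, HF readmission will include patients dying from any cause during the 3 months of FU". On the model: "The treatment effect, on the components, will be investigated by the same statistical model as used for the combined endpoint". On the population, section 5.5 says that for the secondary endpoints "the statistical analyses will be based on the same data set as will be used for the primary endpoint analysis".

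Protocol v2.0 section 10.3 has the same gate and order but a different first component: "For this analysis, HF readmission will include patient dying from HF during the 3 months of FU". Deaths from other causes enter only in a worst-case sensitivity analysis, "assuming a HF readmission for all patients dying to non HF related causes during the 3 month follow-up will be executed".

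SAP section 5.1 describes the plan as "based on the statistical information documented in the study protocol version 2.0 dated 03 January 2019 (see section 10"). It also names the published design paper and regulatory COVID-19 guidance as bases.

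**The concern.** A component analysis exists to show which part of a composite drives its result. Once all deaths are added to HF readmission, nothing separates the component from the composite. Any significant composite would then be followed automatically by a significant result labelled HF readmission, even if the arms differed only in deaths.

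The label matters. Fewer HF readmissions is part of the SAP's own secondary objective, and protocol 10.4 links a 25% reduction in HF rehospitalisation to cost savings. The SAP's stated scope is to "outline the statistical tools used for the primary and secondary objectives of the ADVOR study", yet it specifies no analysis of HF readmission on its own. What the protocol treated as a worst case has become the only version.

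**Working it through.** **1. The identity, which needs no assumed rates.** For each patient let R = HF readmission and D = death from any cause, both within 3 months.

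- Composite (SAP 4.1.3): R or D.
- First component (SAP 5.11.1): R or D.
- First component (protocol 10.3): R or death from HF.
- HF readmission as defined in SAP 4.1.3: R.

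The first two lines are the same variable. Model (logistic, fixed treatment, random centre), data set and 5% level are also the same, so odds ratio, interval and p-value coincide. Hence P(step 1 significant | composite significant) = 100%. In simulated trials the largest difference between the two p-values was 0.

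**2. Trial size used for illustration.** The plan gives a sample size only for the primary endpoint. With 15% versus 25%, two-sided 5% and 80% power:

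(1.960 + 0.842)² × (0.15×0.85 + 0.25×0.75) / 0.10² = 247.2 per arm, about 494 in total; 494 × 1.05 = 518.7, or 519.

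This reproduces the stated 494 and 519. The 519 was split 259 and 260.

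**3. How much of the relabelled component is death alone.** With mortality d, readmission rate r and no correlation, the share of component events that are deaths without readmission is d(1−r)/(d+r−dr). The rates below are assumptions.

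- d = 10%, r = 18%: 0.082/0.262 = 31.3%.
- d = 15%, r = 12%: 0.132/0.252 = 52.4%.
- d = 5%, r = 25%: 0.0375/0.2875 = 13.0%, falling to 9.5% with a death–readmission correlation of 0.3.

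**4. What the step would hide.** Simulation with 20,000 trials per setting and a two-sided 5% chi-square test without the centre effect. Assumed: control readmission 12, 18 or 25%; correlation 0 or 0.3; 30, 50 or 70% of deaths from HF. The last three columns are percentages of trials with a significant composite.

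| Assumed truth | Composite significant | SAP step 1 | Readmission or HF death (protocol) | Readmission alone |
|---|---|---|---|---|
| Only mortality differs (7.5% or 10% vs 15%) | 12–45% | 100% | 20–62% | 5–22% |
| Only readmission falls, by 25%; mortality 5–15% in both arms | 9–35% | 100% | 62–93% | 56–91% |
| Both fall by 25% (mortality 9% vs 12%, or 7.5% vs 10%) | 28–51% | 100% | 57–89% | 44–77% |

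If neither component differs, the composite is significant in about 5% of trials.

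A sharper case uses 259 per arm, readmission 18% and HF death 5% in both arms, non-HF death 10% vs 2%, and independent events. The composite is significant in about 39% of trials. In all of those the SAP would report a significant HF readmission effect, although readmission is unaffected. The protocol version would be significant in about 6% of them.

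**5. Search for a stated reason.** SAP 5.11.1 gives none. The document history gives only the removal of the iron variables for v2.0. The same sentence already stands in SAP v1.0 section 5.11.1, whose entry reads only as a first version. The departure therefore dates from v1.0 and was never explained in the SAP.

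**The case against.** The step is exploratory under SAP 5.3, runs only after a significant composite, and leaves the primary, composite and Cox analyses unchanged. That stands, and it limits the severity.

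The identical step also removes any real gate before mortality. SAP 5.3 claims no multiplicity control, so no promised error rate is broken. In simulated trials with equal mortality in both arms, mortality was both reached and significant in about 1–2% under either definition. This is not material.

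Counting deaths could be defended as a way to handle death as a competing event. The SAP does not say so, and that would not turn a copy of the composite into a separate component. The design paper named in SAP 5.1 might contain the any-cause wording. It could not be consulted, so the supported statement is that the SAP itself gives no reason.

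HF readmission is not lost from the trial plan. Protocol 3.6 keeps it as tertiary endpoint 3, and protocol 10.3 plans recurrent-event models; nothing withdraws either. The gap is in the SAP. Subtracting deaths from composite events would show readmitted survivors by arm, but not all readmitted patients and not a planned comparison.

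Finally, the protocol definition still mixes HF deaths into the component, as the 20–62% in the first row of the table shows. Restoring it reduces the labelling problem without removing it, so readmission alone is needed as well.

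**Conclusion.** The concern holds, and the rule is wrong as written. The first component test in SAP 5.11.1 is the composite under another name, and it passes with probability 1 whenever it is reached. That follows from the documents alone. It departs from protocol 10.3, and the SAP states no reason.

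The size of the possible misreading depends on rates that the documents do not give. Under the assumptions above, 9–52% of events coded as HF readmission would be deaths without a readmission. If only mortality differed, readmission alone would support the SAP's result in about 5–22% of trials with a significant composite. The consequence is limited to labelling and interpretation of a conditional, exploratory step. It should be fixed, but it does not threaten the trial's main conclusions.

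**What to change.** In SAP 5.11.1:

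1. Replace the any-cause sentence with the protocol 10.3 definition (HF readmission or death from HF) and state how deaths of unknown cause are classified.
2. Keep the any-cause version only as the worst-case sensitivity analysis, with a note that it equals the composite.
3. Report HF readmission alone, as defined in SAP 4.1.3, by arm with effect estimate and 95% interval, whether or not the composite is significant. An analysis with death as a competing event is a useful option.
4. Record the departure from protocol 10.3 and its reason, before unblinding if possible.

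The cost is SAP wording, two derived variables and one rule. No new data collection is foreseen: SAP 4.4 has HF readmissions and deaths adjudicated, and protocol 9.4 codes deaths as HF related, non-HF related or unknown. One check is needed. Protocol 9.2 gives criteria for cardiovascular and non-cardiovascular death but none for HF death, and SAP 4.4 does not say that HF-relatedness is adjudicated. The adjudication committee may have to confirm that code. The component will have fewer events and a wider interval.
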